Describe the anticipated frequency and severity of the harms associated with the risks identified above; for example, if you are performing "x" test/assessment, or dispensing "y" drug, how often do you expect an "anticipated" adverse reaction to occur in a study participant, and how severe do you expect that reaction to be?

Expected harm as a result of participating in this study is minimal. Respondents only participate once in the survey. There is no intervention, therefore adverse events are not relevant.

Describe steps to be taken to minimize risks. Include a description of your efforts to arrange for care or referral for participants who may need it.

Interviews will be administered in a private area within the homestead or nearby; respondents will not be required to travel away from their homes in order to participate. The respondents will assist in identifying a suitable location.

Describe the research burden for participants, including time, inconvenience, out-of-pocket costs, and so on.

The only burden for respondents is up to 75 minutes of time spent during the household visit, including the interview. There will be no payments or monetary compensation of study participants since the interviews will be done at their homes.

Describe how participant privacy will be protected during data collection if sensitive questions are included in interviews.

Private locations will be located for interviews to project participant privacy. No sensitive questions, such as HIV status, will be asked.

6. Direct Personal and Social Benefits

Describe any potential direct benefits the study offers to participants ("payment" for participation is not a direct personal benefit).

There will be no direct benefits to individual study participants; they will not receive any payment or other compensation.

Describe potential societal benefits likely to derive from the research, including value of knowledge learned.

It is expected that through the survey information, community level coverage of healthy behaviors and health-seeking practices will improve at the same time that health interventions will be more effectively targeted to the health situation in the community.

7. Payment

No payment or other means of compensation will be made to study participants.

8. Study Management

Oversight Plan

Describe how the study will be managed.

An MCSP studies steering committee will be constituted at the MCSP headquarters comprising the investigators listed in this protocol and other MCSP staff at managerial positions who provide oversight. The committee will meet at least once a quarter to review the status of each in-country KPC study.

What are the qualifications of study personnel managing the project?

The members of the "core team" are as follows: add specific names and qualifications here.

How will personnel involved with the data collection and analysis be trained in human subjects research protections? (Use the JHSPH Ethics Field Training Guide on our website).

All investigators who are members of the Core team have completed CITI training or the equivalent for their organization (ICF International). The local co-investigators and field staff will train in human subjects research protections, by one or more members of core team. The training will follow JHSPH Ethics Field Training Guide and conform to the in-country requirements.

If the PI will not personally be on-site throughout the data collection process, provide details about PI site visits, the supervision over consent and data collection, and the communication plan between the PI and study team.

In situations where the PI is not in a position to visit a study site, one of the core team will visit each site at least twice: once to plan the assessment with the MOH, Jhpiego, USAID, and local counterparts at the start of the assessment for training and to supervise data collection to ensure quality procedures and adherence to human subjects research protocol, and a second time toward the end of data collection to ensure data are

completed and entered and to supervise preliminary analyses and reporting to MOH and counterparts. During interim periods, the research team will conduct teleconferences or email updates every 2 weeks with in-country teams, Jhpiego, and in-country co-investigators.

Recordkeeping

Describe how you plan to ensure that the study team follows the protocol and properly records and stores study data collection forms, IRB regulatory correspondence, and other study documentation.

Safety Monitoring

N/A

Other IRBs/Ethics Review Boards

Approval will be sought from local IRBs in countries that have them. In countries without a local IRB, a letter of approval will be sought by the local Ministry of Health.

Collaborations with Other Institutions

Insert Name of Institutions in Partner column(s); add additional columns if necessary.

	Partner I	Partner 2	
Primary grant recipient			
Collaborator			

For the following, indicate "P" for "primary" and "S" for "secondary" as appropriate to role and level of responsibility. Add additional items if useful.

I	Human subjects research ethics training for data collectors		
2	Day-to-day management and supervision of data collection		
3	Reporting unanticipated problems to the JHSPH IRB/sponsor		
4	Hiring/supervising people obtaining informed consent and/or collecting data		
5	Execution of plan for data security/protection of participant data confidentiality, as described in Section 5.		
6	Biospecimen processing, storage, management, access, and/or making decisions about future use

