- 2. LQAS (lot quality assurance sampling), minimum of 19 interviews per supervision area, minimum of 5 supervision areas
 - a. Parallel sampling
 - b. Without parallel sampling
- 3. Stratified random sampling
 - a. Parallel sampling
 - b. Without parallel sampling

Choosing Clusters

Clusters will be determined by probability proportion to size (PPS). The definition of a cluster may vary country to country. In most cases clusters will be communities in rural areas and neighborhoods in urban areas; however, alternative divisions of populations may be used if appropriate to the country setting. The following are the steps for PPS:

- 1. Create a list (ordered randomly) of communities (or other appropriate division), the population for each, and the total population of all communities (estimates are fine).
- 2. Calculate the cumulative population of each community by summing the total population of the community with the combined total population of all the preceding communities on the list.
- 3. Determine the sampling interval by dividing the total population of the entire program area by the total number of clusters, which is 30 for a 30-cluster survey, a minimum of 95 for LQAS, and a minimum of 96 for stratified.
- 4. Choose a random number to identify the starting point on the list to begin selecting clusters. The random number must be less than or equal to the sampling interval.
- 5. Beginning with the random number, use the sampling interval to identify communities for the clusters (30, 96, or 95).

Household Selection (within a Cluster)

The following are options for household selection.

- 1. In the field, at the time of conducting interviews
 - a. "Spin the bottle"
 - b. Mapping
- 2. With a pre-existing list

In all cases larger clusters should be subdivided before beginning household selection. For urban areas in particular, selection rules must be developed ahead of time on how to handle different housing types, such as high rises or multiple families living in a single dwelling. "Spin the bottle" and mapping are applied at the time of data collection, while using a pre-existing list involves household selection before beginning data collection in the field. For "spin the bottle," the interview team selects the center of the cluster and spins the bottle to determine which direction to go for interviews. Households are selected based on a set (*k*th) interval of households from the center or the nearest neighbor's door.

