For studies that interview women and/or men ages 15–17 years, consent will be obtained from an adult in the household to conduct the interviews or, in the case of emancipated minors (according to local legal definition), they will give their own consent.

Households within each sampled cluster will be visited by the data collectors. Interviewers will ask to speak to an adult (18 years of age or whatever the local legal age of majority is), and if available the interviewers will ask screening questions (and fill out a screening form) to determine whether an eligible mother or father is present in the household. The screening form will be destroyed at the end of the fieldwork. If the answer is yes, and he or she is home and he or she agrees to participate following an informed consent/assent process, then he or she is interviewed. If he or she is not home but expected back within 30 minutes, the interview team will return to the house no more than three times before finishing all the interviews in the area. If unavailable, he or she will be counted as "Non-response" and substituted with someone from another household.

When no eligible mother or father is available in a household, then the interview team proceeds to the next house selected to be visited. If a mother has more than one child age 0–59 months, normally they will be asked about the youngest child. However, for some countries, it can be predetermined to select one of the mother's children at random.

Sample Size Determination

Specific sample sizes will vary from country to country. However, sample sizes will be calculated to provide estimates with confidence levels of 95 percent and precision of 10 percent for key indicators. For stratified random sampling and LQAS the design effect is 1. For 30-cluster sampling a design effect of 2 will be assumed. For all cases, if indicators are to be disaggregated, the total sample size must be multiplied by the number of disaggregation categories; if parallel sampling is needed the sample size must be increased to ensure adequate sample sizes for all indicators collected. Final sample sizes will be powered on the most important indicators, which may result in wider confidence intervals for a few of the other indicators.

For individual studies, decisions will be made regarding the most important indicators for which to collect information. The sample size will be powered for these indicators. After this the study will use the

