appropriate sample size formula based on the chosen sampling methodology. The value of p (proportion) should be .5 (50%) given that these surveys collect information from a variety of indicators with varying proportions in a population, many of which may not be known before the survey is implemented. A p value of .5 gives the maximum sample size needed to estimate any level.

The sample size for a single survey designed to estimate levels at one point in time (not compared with another group) will be determined by the following:

For stratified sampling, simple random sampling, and LQAS:

$$N = Z\alpha^2 pq / d^2$$

- $Z\alpha = 1.96$ corresponding to a confidence level of 95%
- p = 0.5 (maximum sample size)
- q = 1 0.5 = 0.5
- d =accuracy desired = 10% = 0.10
- $N = (1.96)^2 \times 0.5 \times 0.5 / (0.10)^2 = 96$

For 30-cluster sampling, samples size collected from the preceding formula will be multiplied by 2:

$$N_C = N \times \text{deff}$$

Thus, $N_C = 192$

The number of households visited will be calculated based on estimates of the percentage of families expected to have children in the needed age groups. For example, if it is estimated that 45 percent of households have children 0–23 months and 166 eligible mothers must be interviewed, then survey teams may have to visit N_1 =166 × (100 / 45) = 369 households.

Sample sizes for comparison of two phases or groups will use the following formula for stratified random sampling or simple random sampling:

$$N_1 = N_2 = [Z\alpha_{1/2} + Z\beta]^2 [2pq] / (p1 - p2)^2 = [1.96 + 1.28]^2 [2(.5)(.5)] / (.2)^2 = 1.31$$

- N_1 = baseline sample size
- N_2 = final evaluation sample size
- $Z\alpha_{/2}$ is the Z value corresponding to the chosen level of risk α . ($Z\alpha_{/2}$ should be used in two-sided tests, and $Z\alpha$ should be used in one-sided tests.)
- $Z\beta$ is the Z value corresponding to the chosen level of risk β (it directly relates to the "power" of the test as power = 1β ; ($Z\beta$ = 1.28 for a power of .9)
- p_1 is the expected coverage at baseline (can be set to .5 for maximum sample size)

•
$$q_1 = 1 - p_1$$

• p_2 is the expected final coverage (can be set to .5 for maximum sample size)

•
$$q_2 = 1 - p_2$$

- $p = (N_1 p_1 + N_2 p_2) / (N_1 + N_2)$
- q = 1 p

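### At the LQAS floor of 5 areas and 95 interviews, a design effect of 1 and ±10 points hold only if supervision areas are about equal in size, and the cluster-selection rule conflicts with the per-area minimum

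*Protocol*

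**What the plan says.** Protocol section 3, Sampling Methodologies, lists as option 2 "LQAS (lot quality assurance sampling), minimum of 19 interviews per supervision area, minimum of 5 supervision areas". Under Choosing Clusters, the selection is proportional to size for every option, with one interval for the whole program: "Determine the sampling interval by dividing the total population of the entire program area by the total number of clusters". For LQAS that number is at least 95, which at the floor means one interview per cluster.

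Under Sample Size Determination, "sample sizes will be calculated to provide estimates with confidence levels of 95 percent and precision of 10 percent for key indicators". The same part states that "For stratified random sampling and LQAS the design effect is 1" and sizes LQAS with the simple-random formula, giving 96. It attaches no condition on the sizes of the supervision areas, and the six sizing steps that follow contain none.

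Section 4, Study Implementation (item 4), adds that LQAS decision-rule tables are applied to each supervision area, so the number per area has a purpose of its own.

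**The concern.** A design effect of 1 is right for a simple random sample and about right for a sample allocated in proportion to population. Under LQAS at the floor the allocation is fixed by the minimums: five numbers, each at least 19, that add to 95 can only be 19 each. With equal numbers from areas of unequal population, the program-area figure needs population weights, and those weights raise the variance. This is separate from clustering within communities, because there is one interview per cluster. It is also not cured by weighting, because it is the price of weighting.

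At stake is whether the ±10 points that the generic text promises for program-area estimates is a property of the smallest LQAS design it allows. Every country annex that picks this option inherits the design effect from the generic text.

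**Working it through.** **Inputs from the protocol (section 3).** Z = 1.96, "corresponding to a confidence level of 95" percent; p = 0.5; "d =accuracy desired = 10% = 0.10"; H = 5 areas; n_h = 19 per area; n = 5 × 19 = 95. **Assumed:** the population shares w_h, since the documents give none.

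**1. The protocol's own figure.** N = 1.96² × 0.5 × 0.5 / 0.10² = 96.04, stated as 96. It reproduces. With n = 95 and a design effect of 1, the half-width is 1.96 × √(0.25/95) = ±10.05 points, essentially on target. One area alone gives 1.96 × √(0.25/19) = ±22.5 points, so the ±10 can only refer to the program-area estimate.

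**2. Variance with equal numbers per area.** The weighted estimate has variance Σ w_h² p_h(1 − p_h)/n_h. With n_h = n/H and the same coverage p in every area, this is [p(1 − p)/n] × H Σ w_h². The design effect is therefore H Σ w_h², which equals 1 + CV² of the area populations (standard deviation with divisor H).

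**3. Size under assumed shares**, using half-width = 1.96 × √(0.25 × deff / 95):

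| Shares (%) | Σw² | deff = 5Σw² | Half-width (points) |
|---|---|---|---|
| 20/20/20/20/20 | 0.2000 | 1.00 | ±10.05 |
| 26/23/20/17/14 | 0.2090 | 1.05 | ±10.3 |
| 30/25/20/15/10 | 0.2250 | 1.13 | ±10.7 |
| 35/25/20/12/8 | 0.2458 | 1.23 | ±11.1 |
| 40/25/15/12/8 | 0.2658 | 1.33 | ±11.6 |
| 50/20/15/10/5 | 0.3250 | 1.63 | ±12.8 |

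In the 40% case the effective sample is 95/1.329 = 71.5.

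**4. When the loss is absorbed or offset.**
- More areas: H × 19 interviews keep ±10 points up to a design effect of 19H/96.04. That is 114/96.04 = 1.19 for six areas and 133/96.04 = 1.38 for seven.
- Coverage away from 50%: 40/25/15/10/10 shares give deff 5 × 0.265 = 1.325. At p = 0.8 the half-width is 1.96 × √(0.16 × 1.325/95) = ±9.3.
- Coverage that differs between areas: take 30/25/20/15/10 shares with coverage 0.1, 0.3, 0.5, 0.7, 0.9 in that order. Then Σ w_h² p_h(1 − p_h) = 0.03685 and overall coverage is 0.40. The design effect is 5 × 0.03685/0.24 = 0.77, and the half-width is ±8.6. With coverage 0.3, 0.4, 0.5, 0.6, 0.7 the sum is 0.0514 and overall coverage is 0.45. The design effect is 5 × 0.0514/0.2475 = 1.04, and the half-width is ±10.2.

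**5. The selection rule against the minimum.** One interval over the whole program area gives each area about 95 × w_h clusters. With 30/25/20/15/10 shares that is 28.5, 23.75, 19, 14.25 and 9.5, so the two smallest areas fall below 19. A proportional allocation that keeps 19 in the 10% area needs 19/0.10 = 190 interviews. With 95 clusters, the two rules fit together only if each area holds about a fifth of the population.

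**The case against.** The strongest case on the other side has four parts.

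- The text sets minimums, not equal numbers, and nowhere says that supervision areas differ in size. This stands. A reader might infer that LQAS here always takes equal numbers from unequal areas; the documents do not say so. Equal numbers follow only at the 95-interview floor, and unequal sizes are an assumption.
- The program-wide selection step is proportional, which would make the sample self-weighting and remove the loss. Taken alone, that is correct. At 95 clusters, however, it breaks the 19-per-area minimum unless areas are about equal, so it exposes a conflict and does not rescue the stated design effect.
- The factor H Σ w_h² assumes the same coverage in every area. This stands too: with strongly differing coverage the true design effect can fall below 1, as step 4 shows. But the protocol plans at p = 0.5 because coverage is often unknown beforehand, so it cannot count on such an offset at the planning stage.
- Country annexes fix the final sample size. They do, but they choose among options defined in the generic text, where the design effect of 1 is already set.

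A reader might also infer that reported confidence intervals will be too narrow. The protocol uses the design effect only to plan sample size and does not say that intervals will be computed with it. Any analysis plan is not at hand.

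**Conclusion.** The point holds in conditional form and is minor. At 5 areas and 95 interviews, with unequal area populations and similar coverage near 50%, the population-weighted program-area estimate has a design effect of about 1 + CV² of area sizes and misses ±10 points. Under shares from 30/25/20/15/10 to 40/25/15/12/8 the half-width is about ±10.7 to ±11.6. Milder inequality costs a few tenths of a point, and a 50% area would take it to ±12.8. All shares are assumptions.

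The documents do not support the claim that every LQAS survey under this protocol misses its target, nor that the design effect is 1 only when areas are equal. Both depend on the floor, on coverage near 50% and on similar coverage across areas. What needs no assumption about shares is that the text gives two allocation rules which, at 95 clusters, agree only for areas of about equal size, together with a design effect that carries no such condition.

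**What to change.** State under Sampling Methodologies whether LQAS uses a fixed number of interviews per supervision area or program-wide selection proportional to size, and reconcile the Choosing Clusters step with that choice.

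If the number per area is fixed, change the LQAS part of the design-effect sentence in Sample Size Determination to: *for LQAS with equal numbers per area, 1 only if supervision areas have about equal populations; otherwise plan with H × Σ w_h², assuming common coverage, where H is the number of areas and w_h their population shares.* Each annex then computes the factor from its area populations and restates the program-area precision.

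Compute the reported program-area estimate with population weights and its interval from the stratified variance Σ w_h² p_h(1 − p_h)/n_h. The planning factor should not be used for reported intervals, because it would make them too wide where coverage differs between areas.

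If program-wide selection is kept, the total must be large enough for the smallest area to reach 19, or the minimum must be reconsidered.

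For a fixed number per area, the cost is a few sentences and a one-line calculation per annex. No interviews need be added if the precision is restated, but the stated precision becomes slightly less favourable. An annex that wants to hold ±10 points would need about 96.04 × 1.125 = 109 to 96.04 × 1.329 = 128 interviews (rounded up) under the same shares.

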The KPC surveys will be implemented in the 24 priority countries where the USAID-funded MCSP will have a presence as well as other countries where in-country USAID missions buy into MCSP to conduct these studies. This generic protocol will have JHSPH (Johns Hopkins Bloomberg School of Public Health) as the IRB of record; the MCSP consortium partner IRBs (JSI [John Snow International], PATH, PSI [Population Services International]) will receive the final approved version. Country-specific plans detailing the sampling and procedures will be added to this generic protocol as "annexes"; this will be done through submitting amendments of the generic protocol to JHSPH's IRB, reflecting any relevant changes that will be made in order to maintain the annexes added as subsets of the generic protocol.

The KPC is a flexible survey tool that can be tailored for various technical areas and combination of areas while maintaining standards for collection of information for specific interventions. For example, all programs that include control of diarrheal disease will collect information about the percentage of children who had diarrhea in the two weeks preceding the survey, were given oral rehydration solution (ORS), and were given zinc. However, programs that do not focus on diarrhea will not collect information on treatment of diarrhea.

KPC surveys will be repeated at various times during MCSP program implementation in a target country, from annually to every 2–3 years. In most cases surveys will be implemented only in MCSP intervention areas, but if the opportunity exists surveys may also be carried out in comparison areas. Specific details for each country conducting a KPC survey will be added as an annex to this generic protocol.

Justification of Sample Size

In order for the KPC to be adapted to what is needed for specific studies, the design provides for limited choices regarding sampling methodology, household selection, respondent selection, and sample size. Each study amendment will specify which options were chosen to be implemented in the individual study.

Sampling Methodologies

The following are the three options for sampling methodology, each of which can be implemented with or without parallel sampling. All sampling methodologies will include a step of choosing clusters.

- 1. 30-cluster, with number of interviews conducted per cluster varying from 7-30
 - a. Parallel sampling
 - b. Without parallel sampling

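### Shuffling the community list before systematic PPS selection leaves geographic spread to chance: an efficiency loss for the 30-cluster option, and a conflict with the per-area minimum for LQAS

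*Protocol*

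**What the plan says.** Under Choosing Clusters the protocol gives one five-step procedure for all three sampling options. Step 1 is "Create a list (ordered randomly) of communities" with their populations. Step 2 cumulates population down that list. Step 3 is "Determine the sampling interval by dividing the total population of the entire program area by the total number of clusters", which it sets at 30 for the 30-cluster survey, at least 95 for LQAS and at least 96 for stratified sampling. Steps 4 and 5 take a random start within the interval and then select at that interval.

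Under Sampling Methodologies the first option is "30-cluster, with number of interviews conducted per cluster varying from 7-30". The LQAS option requires at least 19 interviews in each supervision area and at least five such areas.

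Under Sample Size Determination, "sample sizes will be calculated to provide estimates with confidence levels of 95 percent and precision of 10 percent for key indicators", and "For 30-cluster sampling a design effect of 2 will be assumed". This gives 192 interviews for a single 30-cluster survey and 262 per round for a comparison of two rounds.

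List order is not among the options that a country annex is invited to choose. It is a fixed step of the generic procedure.

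**The concern.** Systematic selection with a fixed interval stratifies implicitly by the order of the list. Sorted by district and urban/rural status, the list yields a number of clusters in each district close to its population share. Shuffled, it yields numbers that vary by chance, much as in a simple random draw. Nothing else in the 30-cluster option spreads the clusters.

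Two things are at stake. First, any real difference in coverage between areas is left in the sampling error of each round, and therefore in the change between rounds, which the secondary objectives set out to measure. Second, LQAS decision rules are to be applied to each supervision area (Study Implementation), while the written procedure does not control how many clusters an area receives.

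**Working it through.** **The plan's own figures.** N = 1.96² × 0.5 × 0.5 / 0.10² = 96.04, taken as 96; × 2 = 192. For two rounds, (1.96 + 1.28)² × 2 × 0.25 / 0.2² = 131.2, taken as 131; × 2 = 262. Both reproduce.

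**30-cluster option, precision.** Let r be the share of between-cluster variance that lies between areas. The protocol gives no value, so 0–40% is an assumption. Sorting removes roughly that share of the clustering part of the design effect: deff = 1 + (1 − r). Half-width at 192 = 1.96 × √(0.25 × deff / 192). Power at 262 per round = Φ(√(262 × 0.2² / (2 × 0.25 × deff)) − 1.96).

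| r (assumed) | deff | Half-width, points | Power at 262 |
|---|---|---|---|
| 0 | 2.0 | 10.0 | 90% |
| 10% | 1.9 | 9.7 | 91% |
| 20% | 1.8 | 9.5 | 93% |
| 40% | 1.6 | 8.9 | 95% |

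A slightly different form, deff = 2 − m × ICC × r with m = 7 interviews per cluster and ICC = 1/(m − 1) = 1/6, gives 1.88, 1.77 and 1.53 at r = 10%, 20% and 40%. The picture is the same.

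A simulation used an assumed frame of 300 communities of unequal size in 10 districts, 30 clusters of 7 interviews, and 4,000 draws per setting. Design effects, random against sorted order, were:

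- r = 0: 1.84 against 1.83
- r = 10%: 1.75 against 1.72
- r = 25%: 1.86 against 1.61
- r = 50%: 1.77 against 1.34

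The mean error was at most 0.001 in every setting, so neither order biases the estimate.

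**30-cluster option, balance.** In a similar simulated frame (10 districts, about 3 expected clusters each, 3,000 draws), random order left at least one district with no cluster in about 30% of draws; sorted order never did. With 5 districts of about 6 expected clusters, random order put some district 3 or more clusters off its expectation in about 50% of draws; sorted order never did.

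**LQAS.** The minimum number of clusters is 95 = 5 × 19, which implies one interview per cluster. Any split other than exactly 19 in each of five areas therefore leaves some area short. With five areas of 100 equal-sized communities, selection from a shuffled list amounts to simple random sampling, and the chance of exactly 19 in each area is C(100,19)⁵ / C(500,95) = 0.0002, or 0.02%. With 200 communities per area it is also 0.02%. In 3,000 simulated draws with 100 per area, the smallest area received 14.5 clusters on average. With 200 per area, the standard deviation of one area's count is √(95 × 0.2 × 0.8 × 905/999) = 3.7, and its 5th to 95th percentile is 13 to 25.

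Sorting gave 19 in every area in all draws, but only because the areas were equal. An area with 10% of the population would expect 0.10 × 95 = 9.5 clusters, so a sorted list would give it 9 or 10 every time.

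**Cost in variance estimation.** Pairing 30 clusters leaves 15 degrees of freedom instead of 29, so t is 2.13 instead of 2.05. With t in place of 1.96, the half-width at 192 is 10.4 points unsorted. Sorted and paired, it is 10.9 at r = 0, 10.3 at r = 20% and 9.7 at r = 40%.

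**The case against.** For the 30-cluster option the procedure is a valid probability sample. It promises ±10 points with an assumed design effect of 2, and 192 delivers that. Random order protects against periodicity in the list and keeps variance estimation simple, which matters where the protocol permits hand tabulation. The option promises no district estimates, disaggregated indicators require a larger sample, and stratified sampling is offered separately. All of this stands, and it limits the point to efficiency and balance.

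A reader might infer from the Background section that between-area differences are large, and hence that the gain is large. The documents do not support that. Their examples contrast countries, Brazilian states, and education and wealth groups in Bolivia, whereas a KPC survey covers a subnational program area. No figure is given for differences between areas inside one, and a wealth or education gradient is reduced by geographic sorting only where it follows geography. The range must therefore start at no gain.

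On LQAS, it is fair to say that failure is almost built in, because 95 has no slack over 5 × 19, and that 95 is stated as a minimum. More clusters, or extra interviews in short areas, could make up the number, and country annexes will detail sampling. But the written steps compute the interval over the whole program area and contain no rule that secures 19 per area.

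**Conclusion.** The point holds as a modest improvement for the 30-cluster option and as an internal conflict for LQAS.

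For 30 clusters, the gain from sorting runs from nothing to a design effect of about 1.6 and a half-width of about 8.9 points, on an assumed area share of 0–40%. Part of that gain is given back if variance is estimated from pairs. It would go too far to conclude that random ordering biases the estimates or that 192 or 262 is wrong: selection remains proportional to size and both figures stand.

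For LQAS, the minimum of 95 clusters drawn program-wide meets the 19-per-area minimum in about 0.02% of draws, assuming five equal areas and one interview per cluster. It would also be wrong to infer that sorting cures this. Sorting allocates by population, so it works only when areas are of equal size. The remedy there is selection within areas.

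**What to change.** For the 30-cluster option, change step 1 to a list sorted by district, then urban/rural status, then geographic order, and keep the random start and interval. Check the sorted list for periodicity.

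For LQAS and stratified sampling, state that steps 1 to 5 are run separately within each supervision area or stratum, with at least 19 selections in each LQAS area.

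Say how variance will be estimated for the sorted 30-cluster design: by paired clusters (about 15 degrees of freedom), by successive differences, or conservatively by ignoring the sort.

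The cost is the wording of the selection steps and one sentence on variance. No interviews are added. The sort needs each community's district and urban/rural status on the list, and paired or successive-difference variance is more work than the simple formula.
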